**Abnormal Labs:**

Abnormal laboratory values or test results constitute adverse events only if they fulfill at least one of the following criteria:

- they induce clinical signs or symptoms,
- they are considered clinically significant,
- they require therapy.

**Adverse Events (AE):**

The severity grade/Common Toxicity Criteria (CTC) AE grade

- Mild: usually transient in nature and generally not interfering with normal activities
- Moderate: sufficiently discomforting to interfere with normal activities
- Severe: prevents normal activities

If CTCAE grading does not exist for an adverse event, use

1=mild, 2=moderate, 3=severe, 4=life-threatening, CTCAE Grade 5 (death) is not used, but is collected in other CRFs (Study Completion, Death/Survival).

**AE Reporting:**

Its relationship to the:

- Study treatment (no/yes), or
- Investigational treatment (no/yes), or
- The other study treatment (non-investigational) (no/yes), or

- Both or indistinguishable

The relationship will be categorized as follows:

- Unrelated- Clearly due only to extraneous causes, and does not meet criteria listed under possible or probable.
- Unlikely- Does not follow a reasonable temporal sequence from administration. May have been produced by the patient's clinical state or by environmental factors or other therapies administered.
- Possible- Follows a reasonable temporal sequence from administration, but may have been also produced by the patient's clinical state, environmental factors or other therapies administered.
- Probable- Clear-cut temporal association with administration with improvement on cessation of investigational medicinal product or reduction in dose. Reappears upon rechallenge. Follows a known pattern of response to the investigational medicinal product.

Its duration (start and end dates) or if the event is ongoing an outcome of not recovered/not resolved should be reported.

Whether it constitutes a serious adverse event(SAE)

Action taken regarding treatment

### **AE Action:**

All adverse events should be treated appropriately. Treatment may include one or more of the following:

- No action taken (i.e. further observation only)
- [study/investigational] treatment dosage adjusted/temporarily interrupted
- [study/investigational] treatment permanently discontinued due to this adverse event
- concomitant medication given
- non-drug therapy given
- patient hospitalized/patient's hospitalization prolonged

### **AE Outcome:**

- All AE outcomes should be recorded (not recovered/not resolved; recovered/resolved; recovering/resolving, recovered/resolved with sequelae; fatal; or unknown)

### **Serious Adverse Events (SAE)**

An SAE is defined as any adverse event (appearance of (or worsening of any pre-existing) undesirable sign(s), symptom(s) or medical conditions(s) which meets any one of the following criteria (Life-threatening in the context of a SAE refers to a reaction in which the patient was at risk of death at the time of the reaction; it does not refer to a reaction that hypothetically might have caused death if more severe.):

- Is fatal or life-threatening
- Results in persistent or significant disability/incapacity
- Constitutes a congenital anomaly/birth defect
- Requires inpatient hospitalization or prolongation of existing hospitalization, unless hospitalization is for:
  - Routine treatment or monitoring of the studied indication, not associated with any deterioration in condition (specify what this includes)
  - Elective or pre-planned treatment for a pre-existing condition that is unrelated to the indication under study and has not worsened since signing the informed consent
  - Treatment on an emergency outpatient basis for an event not fulfilling any of the definitions of a SAE given above and not resulting in hospital admission
  - Social reasons and respite care in the absence of any deterioration in the patient's general condition
- Is medically significant, i.e. defined as an event that jeopardizes the patient or may require medical or surgical intervention.

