## **Introduction:**

Bullous Pemphigoid (BP) is an autoimmune blistering disease that affects the elderly population. Nearly 3,000 to 5,000 new cases of BP will be diagnosed in the United States each year. (8, 9) The incidence of BP has nearly doubled in the last decade. (9) The risk of BP increases significantly with age where individuals over the age of 90, relative to those 60 or younger, are at a 300 fold increased risk of developing BP. (8) BP is characterized clinically by: skin blistering, severe pruritus or itch, and a decreased quality of life. Due to increased life expectancy in the United States, the rates of BP will likely rise in the future.

The pathogenesis of BP is due to antibodies that target the 180kD and 230kD BP proteins, BPAG2 and BPAG1 respectively. BPAG2 is felt to be the key mediator of disease activity in BP. (10) Neutrophils and their proteases have been shown to play a critical role in the cleavage of BPAG2. (2) Mast cells and other cellular mediators also contribute to the pro-inflammatory environment within and surrounding blisters of BP. (3) However, the prior targeting of mast cells and basophils has resulted in unpredictable disease control. (4) The current treatment for BP is most commonly non-specific immunosuppression, which improves the morbidity but may contribute to sepsis related mortality. (1) One study found that nearly 56% percent of individuals with BP developed infection related complications. (1) The aim of therapy is to either decrease the levels of pathogenic antibody or to decrease the inflammatory response.

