outcome (see [Supplemental 3](#)). Information about common side effects already known about the investigational drug can be found in the package insert. This information will be included in the patient informed consent and should be discussed with the patient during the study as needed. The investigator will also instruct each patient to report any new adverse event (beyond the protocol observation period) that the patient, or the patient's personal physician, believes might reasonably be related to study treatment. This information should be recorded in the investigator's source documents, however, if the AE meets the criteria of an SAE. To ensure patient safety, every SAE (see [Supplemental 3](#) for definition), regardless of suspected causality, occurring after the patient has provided informed consent and after the patient begins taking study drug and until 30 days after the patient has stopped study participation will be recorded and reported to Lilly. Any SAEs experienced after this 30-day period should only be reported to Lilly if the investigator suspects a causal relationship to the study drug. All malignant neoplasms will be assessed as serious under "medically significant" if other seriousness criteria are not met. Medical and scientific judgment will be exercised in deciding whether other situations should be considered serious reactions, such as important medical events that might not be immediately life threatening or result in death or hospitalization but might jeopardize the patient or might require intervention to prevent one of the outcomes listed in SAE. Any suspected transmission via a medicinal product of an infectious agent is also considered a serious adverse reaction. All AEs (serious and non-serious) are captured and recorded, SAEs also require individual reporting (see [Supplemental 3](#)). To ensure patient safety, each pregnancy occurring while the patient is on study treatment must be reported to the sponsor-investigator within 24 hours of learning of its occurrence. The pregnancy should be followed up to determine outcome, including spontaneous or voluntary termination, details of the birth, and the presence or absence of any birth defects, congenital abnormalities, or maternal and/or newborn complications. Pregnancy follow-up should be recorded on the same form and should include an assessment of the possible relationship to the study treatment. Any SAE experienced during the pregnancy and unrelated to the pregnancy must be reported on a SAE form.

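### The protocol states its medically-significant seriousness criterion in two conflicting ways, and the operative version, read literally, makes ordinary treated adverse events SAEs (minor; wrong as written)

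*Combined protocol and SAP*

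**What the plan says.** Two current sections describe when an adverse event is serious because it is medically important.

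- **Supplemental 3, Serious Adverse Events (SAE).** An adverse event is serious if it is one "which meets any one of the following criteria". The last criterion reads "Is medically significant, i.e. defined as an event that jeopardizes the patient or may require medical or surgical intervention".
- **Safety Monitoring (main body).** Important medical events count if they "might jeopardize the patient or might require intervention to prevent one of the outcomes listed in SAE". The decision is discretionary: "Medical and scientific judgment will be exercised in deciding whether other situations should be considered serious reactions". The section also makes every malignant neoplasm serious, and treats suspected transmission of an infectious agent by a medicinal product as serious.

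Safety Monitoring gives Supplemental 3 as the source of the definition, requiring a report of "every SAE (see [Supplemental 3](#) for definition), regardless of suspected causality". SAE Reporting in Supplemental 3 sets the limit at 5 days from learning of the event.

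Two other parts of Supplemental 3 bear on the point. AE Action lists "concomitant medication given" among the ordinary responses to any adverse event. Abnormal Labs makes a laboratory value an adverse event if, among other routes, "they require therapy".

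**The concern.** A seriousness definition has to separate events that are merely treated from events that are grave. The intervention limb in Supplemental 3 does not do this, because most adverse events that receive any treatment could be said to satisfy it. The main body states a narrower limb for the same idea, so the same event can be serious under one section and non-serious under the other.

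Two things are at stake. The first is reporting: each event classed as an SAE goes to the company within 5 days whatever its cause. The second is the meaning of any SAE tally given under clinical safety, which is a listed secondary endpoint. If the classification depends on which section the investigator has open, the tally has no fixed definition.

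**Working it through.** No arithmetic applies, and the plan states no figure to reproduce. The check is a comparison of the two texts, followed by test cases.

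**Step 1: compare the elements.**

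| Element | Supplemental 3 | Safety Monitoring | Broader text |
|---|---|---|---|
| Intervention | Possible need for medical or surgical intervention; purpose not stated | Possible need for intervention to avert a listed serious outcome | Supplemental 3 |
| Jeopardy | The event endangers the patient | The event could endanger the patient | Safety Monitoring |
| Malignant neoplasm | Not listed | Always serious | Safety Monitoring |
| Suspected transmission of an infectious agent | Not listed | Serious | Safety Monitoring |
| Judgment | Not mentioned | Explicitly required | n/a |

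The mismatch runs in both directions.

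**Step 2: decide which text governs.** Safety Monitoring defers to Supplemental 3 for the definition, and Supplemental 3 needs only one criterion to be met. The unqualified intervention limb is therefore operative.

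**Step 3: look for a limit inside Supplemental 3.**

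- The label of medical significance could act as a filter, but the bullet goes on to define the label by the broad wording, so the label has no separate limiting force.
- The exception for emergency outpatient treatment sits under the hospitalization criterion only. It refers to definitions placed above it, whereas the medically-significant bullet comes below.
- The judgment clause appears only in Safety Monitoring.

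**Step 4: test cases.**

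- *Oral candidiasis given an antifungal as an outpatient, with no threat to the patient and no listed outcome in prospect.* Supplemental 3: serious, because medical intervention was needed. Safety Monitoring: not serious. Infection monitoring has the investigator look for candidiasis and cellulitis at every visit, so the case is realistic.
- *A laboratory value that is an adverse event only because it needs therapy.* Supplemental 3: the fact that makes it an adverse event also makes it serious, so the two categories merge. Safety Monitoring: not serious unless it could endanger the patient or the therapy is needed to avert a listed outcome.
- *Suspected transmission of an infectious agent that meets no listed criterion.* Supplemental 3: not serious. Safety Monitoring: serious.

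The two sections give different answers in all three cases.

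**The case against.** The strongest reply is that treatment alone was plainly not meant to make an event serious. Safety Monitoring is current text and supplies both the missing qualifier and the appeal to judgment. AE Action treats medication as an ordinary response and lists it separately from hospitalization. Abnormal Labs calls a value needing therapy an adverse event, not an SAE. The event worksheet records whether intervention was necessary as an item of its own. A careful investigator could read the sections together and classify sensibly.

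This stands as evidence of intent, and it means over-classification is possible rather than certain. It does not cure the text, because the section named as the definition still says something else.

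It is also fair to say that the harm is limited. The error is towards over-reporting and hides no event. All adverse events are recorded with severity, relationship, action and outcome, so 12 patients' events could be reviewed and reclassified.

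A reader might infer more than the documents support:

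- **A size for the inflation.** The Introduction reports that "One study found that nearly 56% percent of individuals with BP developed infection related complications", and it is tempting to apply that to 12 patients. The figure comes from an outside study. The documents do not give its follow-up time, the severity of the infections or the share treated, and some infections would be serious under either wording.
- **Dilution of truly serious events, or lost comparability with outside data.** With 12 patients, individual review is feasible. The SAP specifies no comparison of SAE rates with other ixekizumab or bullous pemphigoid data.
- **Disagreement between sites.** The study is single-center.

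**Conclusion.** The point holds as a conflict between two current passages: the criterion is wrong as written, and the severity is minor. Read literally, the operative definition turns ordinary treated adverse events into SAEs with a 5-day report. It also omits two categories that the main body calls serious.

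The possible effects are extra reports and an inflated SAE tally within the secondary safety endpoint. The size cannot be estimated, because the documents give no adverse event rates for this trial. The primary endpoint, the sample size and every analysis specified in the SAP are untouched.

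The conclusion rests on one assumption: that the investigator applies Supplemental 3 as written, as the cross-reference directs. If the Safety Monitoring wording is applied in practice, the over-classification does not arise, but the written definition still needs correcting.

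**What to change.** Reconcile the two sections into one definition. Replace the last bullet of the SAE definition in Supplemental 3 with the complete Safety Monitoring rule:

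1. Important medical events are serious if they could endanger the patient, or could need intervention to avert one of the other listed outcomes.
2. The decision is made by medical and scientific judgment.
3. Malignant neoplasms are serious.
4. Suspected transmission of an infectious agent by a medicinal product is serious.

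Add one sentence saying that needing treatment does not by itself make an event serious. All four elements should be carried over; moving only the intervention qualifier would leave the sections in disagreement.

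The cost is one bullet, one added sentence and matching guidance on the SAE form. No new data are needed. Any events already classified can be rechecked from the recorded adverse event details.

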### **SAE Reporting:**

To ensure patient safety, every SAE, regardless of causality, occurring after the patient has provided informed consent and until 30-days after the subject stopped study participation must be reported to the Lilly as soon as

possible but no later than 5 days from learning of its occurrence according to the Mayo Clinic IRB policy. Any SAEs experienced after the 30-days period should only be reported to Lilly and the Mayo Clinic IRB if the investigator suspects a causal relationship to study treatment. Recurrent episodes, complications, or progression of the initial SAE must be reported as follow-up to the original episode, regardless of when the event occurs. This report must be submitted as soon as possible but no later than 5 days from the investigator receiving the follow-up information. SAE should be followed up until resolution or until it is judged to be permanent. An SAE that is considered completely unrelated to a previously reported one should be reported separately as a new event.

Information collected on the adverse event worksheet (and entered in the research database):

- Subject's name:
- Medical record number:
- Disease/histology (if applicable):
- The date the adverse event occurred:
- Description of the adverse event:
- Relationship of the adverse event to the research (drug, procedure, or intervention):
- If the adverse event was expected:
- The severity of the adverse event:
- If any intervention was necessary:
- Resolution: (was the incident resolved spontaneously, or after discontinuing treatment)
- Date of Resolution:

If the SAE is not previously documented in the Package Insert (new occurrence) and is thought to be related to the investigational treatment further reporting by the investigator to the Health Authority may be required

#### **Supplemental 4: Corticosteroid Rescue**

Subjects will be evaluated at baseline and at 2 week follow ups for disease activity and severity. Those individuals scoring greater than 20 on the BPDAI pruritus component- VAS will be offered oral corticosteroids as follows:

- Corticosteroid Taper
  - Baseline
    - If BPDAI pruritus component- VAS greater than 20
      - Offer oral prednisone 20mg daily
      - If patient declines prednisone for any reason other than disease control this should be documented in the eCRF
  - At 2 week follow ups
    - If BPDAI pruritus component- VAS greater than 20
      - If prednisone naive
        - Offer to continue prednisone at 20mg daily
        - If patient declines prednisone for any reason other than disease control this should be documented in the eCRF
      - If currently on prednisone 20mg daily
        - Maintain on 20mg prednisone daily
        - If patient declines or decides to stop prednisone for any reason other than disease control this should be documented in the eCRF
      - If currently on 20mg prednisone every other day
        - Offer to increase prednisone at 20mg daily
        - If patient declines or decides to stop prednisone for any reason other than disease control this should be documented in the eCRF
    - If BPDAI pruritus component- VAS less than 20
      - If at 20mg daily
        - Taper prednisone to 20mg every other day

- If patient declines or decides to stop prednisone for any reason other than disease control this should be documented in the eCRF
  - If at tapered dose of 20mg every other day
    - Stop prednisone
    - If patient declines or decides to stop prednisone for any reason other than disease control this should be documented in the eCRF
- Calcium 1200mg and Vitamin D 800 IU will be prescribed along with oral corticosteroids and will be continued for the duration of the study once initiated
